7 TRIAL PROCEDURES

7.1 Recruitment

Suitable clients will be identified within the GMMH Perinatal Service. The GMMH Perinatal Service comprises three 'clusters' covering the area of Greater Manchester. The Chief investigator ([name]) works in cluster 3 and to prevent any conflict of interest clients will not be recruited from that cluster.

Recruitment can occur at any point during a client's involvement with the GMMH perinatal service.

Perinatal professionals will use inclusion / exclusion criteria in deciding whom to approach and will ask the client if they have an interest in the study.

Suitable clients who express an interest will be asked by the professional within their cluster if they would like to know more about the research and will be given a Client Invitation Letter. If they decline they will not be asked about, or involved in, any further parts of the research study.

Clients who read the invitation letter and express an interest will be asked if their details can be passed on to the lead researcher for further contact regarding the nature of the study. They will be asked if they would like to be initially contacted by telephone or by email. All clients who express an interest will be sent a Participants' Information Sheet (PIS) outlining the study by email or postal mail. Clients who agree to be contacted by telephone will also have the option to reply via email or by paper slip. Clients who do not wish their details to be passed on to the lead researcher will not be contacted again regarding the study.

Contact with the lead researcher will allow a detailed explanation about the research and the opportunity for the client to ask further questions or clarify the PIS. Clients will be asked if they wish to participate in Cognitive Behavioural Group Therapy (CBGT). They will be aware they can withdraw at any time without any penalty or change to their ongoing involvement with the GMMH Perinatal Service.

A time frame and expected starting date will be discussed with the clients. Clients will be given as much time as they need (minimum 24 hours, maximum 7 days) to consider participation in the research. Clients will have options of replying by email, by post, by telephone or asking the lead researcher to ring them after a set time of their choosing. They can also use these contact points for further clarification or to ask questions.

Clients will not be under any pressure to participate in the research. They will be made aware they can withdrawal from the research at any point. They will be made aware that involvement, or non-involvement with the research will in no way affect their treatment and care plan within the perinatal CMHT. There will be no need for the researcher to have personal data until the patient has agreed to the contact from the researcher.

If a client agrees to participation in the research they will meet with the lead researcher. The client will be asked to sign a written consent form. The client will be under no obligation to sign this and is free to leave the process at this stage. The client will then undertake a clinical assessment with the lead interviewer. This will compose a psychiatric history to confirm their diagnosis. This will also allow inclusion and exclusion criteria to be reviewed. A risk assessment will take place.

7.1.1 Participant identification

Clients will be identified by perinatal professionals (care co-ordinators, community mental health nurses, social workers, specialist mental health midwives, psychiatrists and psychologists) working in Cluster 1 (Central and South Manchester, Trafford and Stockport) and Cluster 2 (Salford, Bury, Bolton and Wigan). Lead perinatal professionals from Cluster 1 and Cluster 2 have been consulted about the research study and are supportive of the project and this approach. The research proposal has been consulted with the psychological leads for GMMH Perinatal Services ([name] and [name]

[name]) the Perinatal consultants for Cluster 2 and Cluster 1 respectively ([name] and [name]) and the Perinatal lead for the GMMH service ([name]).

7.1.2 Screening

Participants will be clients in a secondary care service, the GMMH Perinatal Service.

Clients will have diagnoses recorded by the perinatal service in the ICD 10 categories of F32-33 (depression), F40-41 (anxiety) or F53 (Mental and Behavioural disorders associated with the puerperium, including postnatal depression).

7.1.3 Payment

No payments are made or allocated in this research study.

7.2 Consent

If a client agrees to participation in the research they will meet with the lead researcher via either video conference or telephone link. If necessary this appointment can take place physically face to face however this is dependent on pandemic rules and GMMH trust pandemic guidance. The client will be asked to sign a written consent form. The client will be under no obligation to sign this and is free to leave the process at this stage.

Consent will be obtained by the chief investigator at the assessment meeting to allow access to identifiable personal information (relevant to the research) within the client's PARIS (trust electronic) records.

Consent will also be sought if relevant professionals need to be consulted for relevant information (for example social workers, health visitors, obstetricians or specialist midwives if required).

7.2.1 General Practitioner informed

When a client agrees to participate in the project and gives consent the Chief Investigator will send a letter to their General Practitioner informing them of this.

7.3 Baseline data

The following data will be recorded for clients.

Maternal and Pregnancy Related Variables: Age (within an age range for example 30-34, 35-39), their ethnicity, total previous pregnancies, medication, mental health diagnosis, physical health status

Infant Variables: pregnancy / postnatal status

The client will undertake a clinical assessment with the Chief investigator. This will compose a psychiatric history to confirm their diagnosis. This will also allow inclusion and exclusion criteria to be reviewed. A risk assessment will take place.

7.4 Research Intervention

When ten clients (minimum six) complete this process a convenient time and start date will be arranged to commence the therapy sessions. Each therapy session will have a duration of two hours and take place at approximately at the same time each week for ten weeks. There will be a follow up session at eight weeks.

Each session will be led by two professionals with experience of CBT therapy. The Chief Investigator (an experienced consultant perinatal psychiatrist with a postgraduate qualification in CBT) and a higher trainee psychiatrist (this signifies a trainee who has completed a minimum of 3 years core psychiatry

training involving 'short' and 'long' cases in psychotherapy and achieved successful membership of the Royal College of Psychiatrists requiring examination in various therapeutic techniques including CBT).

The treatment intervention for this research study is Cognitive Behavioural Group Therapy (CBGT). Group sessions will follow an adaptation of models outlined in:

Söchting, I., 2014. Cognitive Behavioral Group Therapy: Challenges And Opportunities

Wenzel, A. and Kleiman, K., 2015. Cognitive Behavioral Therapy For Perinatal Distress.

Additional utilisation of relevant journal articles and texts will also be adapted and referenced as required.

The group is a transdiagnostic group, meaning it includes different diagnoses: depression, anxiety syndromes and postnatal depression. Therefore reference will be made to McEvoy and Nathan, 2007 Effectiveness of cognitive behavior therapy for diagnostically heterogeneous groups: A benchmarking study and Hamilton et al., 2012 Exploring the Effectiveness of a Mixed-Diagnosis Group Cognitive Behavioral Therapy Intervention Across Diverse Populations.

Each session will use CBT techniques. A complete Session outline is available in the Interview Schedule.

The follow up session will review progress or setbacks made to that point, give encouragement and reinforce therapeutic techniques used. It will also aim to troubleshoot any problems with CBT techniques learnt.

CBGT sessions will be understood to take place in clients' homes in a quiet room for the two hour period. Babies will be encouraged to attend as evidence indicates the presence of infants is a key factor for the woman experiencing positive change (Væver, 2015). The presence of an infant will also help to normalise the experience for all the women in the group. There will be a scheduled break at 60 mins and unscheduled breaks will be expected and accommodated (for example the need to change a nappy). Breastfeeding is also encouraged and there is the option to turn her camera off during that period for more privacy.

7.5 Research intervention Outcome Measures

Prior to each session clients will complete the following outcome measures.

- The Edinburgh Postnatal Depression Scale (Cox, Holden and Sagovsky, 1987),
- GAD-7 anxiety scale (Spitzer, Kroenke, Williams and Löwe, 2006)
- Core 10 short measure (Barkham et al., 2013).

These scales will be sent by either email or physical post to the clients to allow them to complete them.

A CORE-OM will be completed prior to the first session and following the final session, again sent by email or physical post. Data from these will be collated for the purpose of the research.

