	Email: [contact]
Funder(s)	[name] MBChB, MRCpsych
	Consultant Perinatal Psychiatrist
	[name]
	[name]
	[contact]
	Email: [contact]
Key Protocol Contributors	[name]
	[name]
	[name]

i. LIST of CONTENTS

GENERAL INFORMATION	Page No.
HRA PROTOCOL COMPLIANCE DECLARATION	1
TITLE PAGE	2
SIGNATURE PAGE	3
KEY TRIAL CONTACTS	4
i. LIST of CONTENTS	5
ii. TRIAL SUMMARY	6
iii. FUNDING	7
v. ROLE OF SPONSOR AND FUNDER	7
vi. ROLES & RESPONSIBILITIES OF TRIAL MANAGEMENT COMMITTEES, GROUPS AND INDIVIDUALS	7
vii, PROTOCOL CONTRIBUTERS	8
viii. KEYWORDS	8
ix. TRIAL FLOW CHART	8
SECTION	
1. BACKGROUND	9
2. RATIONALE	10
3. OBJECTIVES AND OUTCOME MEASURES/ENDPOINTS	12
4. TRIAL DESIGN	13
5. TRIAL SETTING	13
6. PARTICIPANT ELIGIBILITY CRITERIA	14
7. TRIAL PROCEDURES	15
8. STATISTICS AND DATA ANALYSIS	19
9. DATA MANAGEMENT	19
10 ETHICAL AND REGULATORY CONSIDERATIONS	20
11. DISSEMINATION POLICY	23
12. REFERENCES	23
13. APPENDICIES	27

ii. TRIAL SUMMARY

Trial Title	Cognitive Behavioural Group Therapy treatment via a Video Communications Platform for Perinatal Anxiety and Depression: A Case Series							
Internal ref. no. (or short title)	Telecommunication CBGT treatment for Perinatal depression and anxiety.							
Trial Design	Case Series							
Trial Participants	This is a Case Series researching a group of women with common characteristics i.e. within the perinatal period, fulfilling diagnostic criteria of ICD 10 categories F32-33 (depression), F40-41 (anxiet or F53 (Mental and Behavioural disorders associated with the puerperium, including postnatal depression).							
	Those who are asked to take part will be 18 years or older and be clients of the GMMH Perinatal Service. By the nature of this service clients will be in their reproductive years and therefore an inclusion age group of 18-50 will be used.							
Planned Sample Size	Ten (minimum six)							
Treatment duration	Ten sessions (one per week for te	en weeks)						
Follow up duration	One follow up session eight weeks following the last session							
Planned Trial Period	01/03/21 - 30/02/22							
	Objectives	Outcome Measures						

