3.2 Secondary objectives

A Likert Scale Questionnaire (five questions) with an option for free text, will be asked at the final session. This will allow feedback on the group.

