3.3.4 Table of endpoints/outcomes

Objectives	Outcome Measures	Timepoint(s) of evaluation of this outcome measure (if applicable)
Primary Objective To monitor the change in outcome measure scales over	Edinburgh Postnatal Depression Scale, GAD-7 anxiety scale and CORE-10 scale	The scales will be scored at each CBGT session and the follow up session.
the course of the Cognitive Behavioural Group Therapy.	CORE-OM scale	The CORE-OM scale will be scored at the first and final session.
Secondary Objectives To allow participants to give basic feedback on the group	A Likert scale (with free text availability) asking five questions.	Completed at the follow up session

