7.6 Follow-up assessments

Following the ten session group therapy, the group will have one follow up session eight weeks later. This will allow a review and reflection on Cognitive Behavioral Techniques undertaken over the ten week course. Clarifications and questions can also be answered within this session.

All clients will remain under with the Perinatal Service for the duration of the research. On conclusion of the research clients will either remain with their perinatal treatment plan, be signposted to relevant

perinatal support services, have the option for further therapy, or return to Primary Care. This decision will not be influenced by the research study. This decision will be made as a collaborative choice between client and their GMMH perinatal professional / Multi-Disciplinary Meeting.

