7.7 Qualitative assessments

This trial is primarily Quantitative.

A Likert Scale Questionnaire (5 questions) with an option for free text will be asked at the 8 week follow-up session. The scale is as follows:

Strongly Agree Agree Neither Agree Nor Disagree Disagree Strongly Disagree

The questions are as follows

- 1. The Cognitive Behavioural Therapy Group met my expectations
- 2. I would be willing to bring my baby to a Cognitive Behavioural Therapy Group
- 3. Cognitive Behavioural Group therapy is appropriate for mothers like me
- 4. The Cognitive Behavioural Therapy Group allowed me to build networks with other mothers
- 5. I would recommend Cognitive Behavioural Therapy Group to another client

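### EPDS, GAD-7 and CORE-10 have no score after session 10 until the eight-week follow-up, so the four primary scales do not share an end-of-treatment time point

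*Protocol*

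**What the plan says.** **Outcome.** Protocol section 3.3.1 defines the primary outcome as change in EPDS, GAD-7, CORE-10 and CORE-OM across the group course, the aim being lower scores for each woman.

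**Schedule.** Section 7.4 has the sessions "take place at approximately at the same time each week for ten weeks". Section 7.6 adds: "Following the ten session group therapy, the group will have one follow up session eight weeks later". The Trial Summary agrees: "One follow up session eight weeks following the last session".

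**EPDS, GAD-7 and CORE-10.** Section 7.5: "Prior to each session clients will complete the following outcome measures". The Trial Summary says the same. The table in section 3.3.4 adds the follow-up session. Sections 3.1 and 3.3.4 speak more loosely of completion or scoring at each session.

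**CORE-OM.** Section 7.5: "A CORE-OM will be completed prior to the first session and following the final session". The Trial Summary and section 3.1 agree. The table in section 3.3.4 has: "The CORE-OM scale will be scored at the first and final session".

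**Likert questionnaire.** Section 3.2 says it "will be asked at the final session", but section 7.7 says it "will be asked at the 8 week follow-up session". The Trial Summary and the table in section 3.3.4 also place it at the follow-up.

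**The concern.** A measure completed before a session cannot reflect that session. Three of the four primary scales are only ever completed before sessions, so none of them is measured once the full course has been delivered, until eight further weeks have passed. CORE-OM alone is placed after the last treatment session.

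Two things follow. First, for three scales the reader must choose between a score that leaves out session 10 and one that adds eight weeks without group sessions. Neither is change over exactly the course. Second, the four components of one primary outcome cover different amounts of treatment. In a single group of six to ten women with no comparator, within-woman change is the main quantitative evidence, so the points between which it is measured should be clear and common to all scales. This is a matter of data collection, which no analysis plan can repair afterwards.

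The label 'final session' adds a smaller problem. It is not defined, and section 3.2 applies it to a questionnaire that three other places assign to the follow-up.

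**Working it through.** The protocol gives no figure to reproduce here. The check is to lay out the schedule and count.

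**Inputs.** Ten weekly sessions (section 7.4); follow-up eight weeks after the last of them (Trial Summary, section 7.6); three scales before each session (section 7.5) and also at follow-up (section 3.3.4); CORE-OM twice (section 7.5).

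**Timeline**, with session 1 as week 0:

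- Session k falls at week k − 1, so session 10 falls at week 10 − 1 = 9.
- Follow-up falls at week 9 + 8 = 17.

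| Time | EPDS, GAD-7, CORE-10 | CORE-OM | Sessions received by then |
|---|---|---|---|
| Before session 1 (week 0) | yes | yes | 0 |
| Before sessions 2 to 9 (weeks 1 to 8) | yes | no | 1 to 8 |
| Before session 10 (week 9) | yes | no | 9 |
| After session 10 (about week 9) | **no** | yes | 10 |
| Follow-up (about week 17) | yes | no | 10, plus eight weeks |

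**Sessions covered by the in-course change.** For the three scales, 10 − 1 = 9 of 10 sessions (90%). For CORE-OM, 10 of 10.

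**Time points per repeated scale.** 10 + 1 = 11 now; 11 + 1 = 12 with a completion after session 10.

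**Scale forms per woman** (Likert questionnaire not counted). Now 11 × 3 + 2 = 35. With the three scales added after session 10, 35 + 3 = 38.

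**Which visit is the 'final session' for CORE-OM?** The table in section 3.3.4 uses that term for CORE-OM and names the follow-up session separately for the other scales and for the Likert questionnaire. The Trial Summary draws the same distinction between the CORE-OM and Likert timings, and it dates the follow-up from the last session. Both point to session 10.

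**Which visit for the Likert questionnaire?** Three places (Trial Summary, sections 3.3.4 and 7.7) say follow-up. Section 3.2 either uses 'final session' to mean the follow-up, in a different sense from the CORE-OM text, or contradicts the other three. Either way its wording has to change.

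**The case against.** The strongest reply is that little is lost. Each of the three scales has ten weekly scores and a follow-up score. The last weekly score comes shortly before session 10, and the follow-up score comes after all ten sessions. Section 8 plans only frequencies and associations, so no test or fixed contrast is invalidated. Completing measures before each session is a coherent way to track progress, and a twelfth time point improves the schedule rather than correcting an error.

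Most of this stands, and it limits the point to a modest one. It does not remove it: the three scales still lack a score taken when the course has just ended, and CORE-OM has one. The looser wording in sections 3.1 and 3.3.4 does not supply the missing score either, because section 7.5 states explicitly that completion comes first.

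A reader might go further and infer from section 3.2 that the second CORE-OM could fall at the follow-up. Its interval would then be 17 weeks instead of 9, and it would mix change during treatment with eight weeks after it. The documents do not support this. It would let one phrase about a different instrument override the Trial Summary and section 3.3.4, both of which keep the 'final session' and the follow-up apart. A wording slip in section 3.2 is the likelier explanation. Likewise, the difference between CORE-OM being scored at a session (section 3.3.4) and completed after it (section 7.5) is loose table wording and carries little weight.

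**Conclusion.** The point holds in a limited form. EPDS, GAD-7 and CORE-10 have no score reflecting all ten sessions until about eight weeks after session 10, so the four scales of the primary outcome do not share an end-of-treatment time point. The size is one session in ten. How many scale points that session is worth cannot be derived from the protocol; if change accrued evenly across sessions, the in-course score would capture 90% of it.

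This rests on two assumptions: that the forms are completed before each session, as section 7.5 says, and that the CORE-OM 'final session' is session 10, which is a strong inference because the term is undefined. No sample size, error rate or planned test is affected. The change is worth making because it is cheap and the missing score cannot be obtained later.

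The conflict over Likert timing between section 3.2 and the Trial Summary, section 3.3.4 and section 7.7 is a separate wording correction.

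**What to change.** 1. In section 7.5, send EPDS, GAD-7 and CORE-10 together with the CORE-OM already sent after session 10, and name this the end-of-treatment assessment for all four scales. Carry it into the Trial Summary and sections 3.1 and 3.3.4.
2. Replace 'final session' with 'session 10' or 'follow-up session' wherever it appears: the Trial Summary and sections 3.1, 3.2, 3.3.4 and 7.5. In section 3.2, bring the Likert timing into line with the Trial Summary and sections 3.3.4 and 7.7.
3. In sections 3.1 and 3.3.4, say that the three scales are completed before each session, as section 7.5 does.

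**Cost.** Three more short self-report forms per woman (35 to 38), by the existing email or postal route and with no extra visit, plus wording edits. The downside is a slightly greater burden on participants. The weekly pre-session series is unchanged.

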7.6 Follow-up assessments

Following the ten session group therapy, the group will have one follow up session eight weeks later. This will allow a review and reflection on Cognitive Behavioral Techniques undertaken over the ten week course. Clarifications and questions can also be answered within this session.

All clients will remain under with the Perinatal Service for the duration of the research. On conclusion of the research clients will either remain with their perinatal treatment plan, be signposted to relevant

perinatal support services, have the option for further therapy, or return to Primary Care. This decision will not be influenced by the research study. This decision will be made as a collaborative choice between client and their GMMH perinatal professional / Multi-Disciplinary Meeting.

7.7 Qualitative assessments

This trial is primarily Quantitative.

A Likert Scale Questionnaire (5 questions) with an option for free text will be asked at the 8 week follow-up session. The scale is as follows:

Strongly Agree Agree Neither Agree Nor Disagree Disagree Strongly Disagree

The questions are as follows

- 1. The Cognitive Behavioural Therapy Group met my expectations
- 2. I would be willing to bring my baby to a Cognitive Behavioural Therapy Group
- 3. Cognitive Behavioural Group therapy is appropriate for mothers like me
- 4. The Cognitive Behavioural Therapy Group allowed me to build networks with other mothers
- 5. I would recommend Cognitive Behavioural Therapy Group to another client

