Primary	This research aims to explore the efficacy of Cognitive Behavioural Group Therapy (CBGT) via a Video Communications Platform (Microsoft TEAMS) as a means to reduce maternal anxiety and low mood during the perinatal period.	Prior to each session clients will complete the following outcome measures. The Edinburgh Postnatal Depression Scale (Cox, Holden and Sagovsky, 1987), the GAD-7 anxiety scale (Spitzer, Kroenke, Williams and Löwe, 2006) and the Core 10 short measure (Barkham et al., 2013). A CORE-OM will be completed prior to the first session and following the final session. Data from these will be collated for the purpose of the research.						
		A Likert Scale Questionnaire (5 questions) with an option for free text will be asked at the follow-up session.						
Secondary	Not applicable							

iii. FUNDING AND SUPPORT IN KIND

FUNDER(S)	FINANCIAL AND NON FINANCIALSUPPORT
(Names and contact details of ALL organisations providing funding and/or support in kind for this trial)	GIVEN
Funded by Chief Investigator	Not applicable

iv. ROLE OF TRIAL SPONSOR AND FUNDER

The sponsor for this study is the Greater Manchester Mental Health NHS Foundation Trust. Sponsor takes the responsibility for oversight and management of the study. Trial design, conduct, data analysis and interpretation and manuscript writing are the responsibility of the Chief Investigator. Dissemination of the results of the study will be the responsibility of the Chief Investigator under educational supervision by the sponsor. Mothers who are pregnant or have a child under 12 months old will contribute regarding the outcomes of the study and will receive study results.

v. ROLES AND RESPONSIBILITIES OF TRIAL MANAGEMENT COMMITEES/GROUPS & INDIVIDUALS

The research study has a Chief investigator ([name]), clinical supervisor ([name]), university supervisor ([name]) and one co facilitator [name]). For data relating directly to the research study the Chief Investigator ([name]) will have access to this. Clients will be consented for this.

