3.3.2 Secondary endpoints/outcomes

Secondary Outcome

The Likert Scale Questionnaire will allow feedback by the participants on the group.

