10.6 Data protection and patient confidentiality

To ensure any identifying material is excluded each participant will be allocated a pseudonym and an anonymous number when they enter the study. Any quotes will be subsequently attached to this number or pseudonym when recorded as part of the study rather than the participant's name.

The pseudonym will have no identifying demographic or direct clinical information. This link between pseudonym and client will be stored on the Chief investigator's encrypted trust laptop.

Access to personally identifying study data will be restricted to the Chief investigator.

Anonymised data may be shared between [name] and [name] (higher trainee in psychiatry) via secure, password protected email. This will be for the purpose of facilitating the group and planning each CBT session. No files containing identifying patient details will be transferred electronically.

Anonymised findings may be discussed in the course of supervision between the Chief investigator ([name]), clinical supervisor ([name]) and university supervisor ([name]).

A database will be created to store clinical information (e.g. number of CBT sessions, goal for therapy, details of treatment, cognitions, helpful factors of CBGT) which will be linked to clients' pseudonyms / number. The database will be securely stored in a password protected document on the Chief investigator's secure trust computer and trust approved AES 256-BIT encrypted flash drive.

Data relating to the research study will be kept in accordance with GMMH Standard Operating Procedure (RDSOP21 – Retention of Data, Off-site Archiving and Destroying of Documents). Electronic archiving will be undertaken for a retention period of 5 years from completion of study or submission of final report.

If a client contributes information clinically relevant to their perinatal care, this will be recorded on the GMMH electronic trust record 'PARIS'. Furthermore, as outlined, the Chief investigator will complete a paragraph summary of each client's session and upload this to PARIS. This will cover participant's attendance at the group, the headline theme of that CBGT session and a brief risk assessment. Once uploaded this information will remain on PARIS as part of the participant's clinical record.

The Chief investigator will be the data custodian.

10.7 Financial and other competing interests for the Chief investigator, PIs at each site and committee members for the overall trial management

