There are no ownership interests, commercial ties or noncommercial potential conflicts.

Participants are identified from Cluster 1 and Cluster 2 GMMH Perinatal services. They will not be identified from cluster 3 perinatal services ([name] cluster) to prevent any clinical conflict of interest.

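### The only secondary outcome, five-item feedback on the group, is asked at a session led by the therapists with no anonymous return stated, which risks favourable answers of unknown extent

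*Protocol*

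**What the plan says.** Section 3.3.2 gives one secondary outcome: "The Likert Scale Questionnaire will allow feedback by the participants on the group". Section 7.7 fixes the occasion: "A Likert Scale Questionnaire (5 questions) with an option for free text will be asked at the 8 week follow-up session". It lists five statements on a five-point agreement scale. They cover expectations met, willingness to bring a baby, suitability for mothers like the respondent, building networks, and recommending the group.

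Section 7.4 says of the sessions: "Each session will be led by two professionals with experience of CBT therapy". These are the chief investigator and a higher trainee in psychiatry. Section iv adds: "Trial design, conduct, data analysis and interpretation and manuscript writing are the responsibility of the Chief Investigator".

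On identification, section 10.6 says: "To ensure any identifying material is excluded each participant will be allocated a pseudonym and an anonymous number when they enter the study". The same section keeps the link between pseudonym and woman on the chief investigator's laptop.

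On interests, section iii records "Funded by Chief Investigator", section 1 says the research is part of a master's programme, and section 10.7 declares: "There are no ownership interests, commercial ties or noncommercial potential conflicts".

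The timing is not consistent. Section 3.2 says: "A Likert Scale Questionnaire (five questions) with an option for free text, will be asked at the final session". The trial summary, the table in 3.3.4 and section 7.7 all place the questionnaire at the follow-up session.

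**The concern.** Women are asked whether the group met their expectations and whether they would recommend it, on an occasion run by the people who delivered it. The chief investigator takes consent, confirms the diagnosis, leads therapy, can link study records to individuals and writes the report. The co-facilitator is not an independent collector, because section v says the chief investigator supervises him.

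In that setting some respondents may answer out of courtesy. Because every item is worded in the group's favour, a tendency to agree pushes all five in the same direction, and no reverse-worded item would reveal it. At stake is whether a reader can take a high level of agreement as the women's opinion of the group. The declaration in 10.7 adds to this, since a reader relying on it would not be alerted to the overlap of roles.

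**Working it through.** The protocol gives no figure for this outcome, so there is none to reproduce. The check sets the sections side by side and adds simple proportions for scale.

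**1. Status of the questionnaire.** Sections 3.2, 3.3.2 and 3.3.4 make it the sole secondary item. The trial summary puts it in the primary row and marks secondary as not applicable. These need to agree.

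**2. Timing.** Three places say the follow-up session (trial summary, 3.3.4, 7.7) and one says the final session (3.2). Section 3.1 times the CORE-OM by the final session, and the trial summary counts the follow-up from the last of the ten weekly sessions. Section 3.2 can therefore be read as session ten, eight weeks earlier than the other three.

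**3. Mode of completion.** Section 7.5 has the EPDS, GAD-7 and CORE-10 emailed or posted and completed before each session. Section 7.7 states no mode, collector or route of return for the Likert form. Section 3.1 nevertheless describes the same three scales as completed at each session, so in this protocol that phrase can simply mark a timepoint. In-session answering is therefore possible but not established.

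**4. Identifiability.** Section 10.6 provides for a pseudonym and number, so answers need not carry a name. The chief investigator holds the key. The responses are thus pseudonymised, and linkable by the lead therapist.

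**5. Direction of the items.** All five statements in 7.7 favour the group, so agreement is approval on each. None mentions a therapist.

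**6. Scale of a single answer.** The planned number is ten, with a minimum of six. One respondent contributes 1/n to the proportion agreeing:

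| Respondents | One answer changes | Two answers change |
|---|---|---|
| 10 | 1/10 = 10.0 points | 2/10 = 20.0 points |
| 6 | 1/6 = 16.7 points | 2/6 = 33.3 points |

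The protocol stops the trial only above 75% dropout (section 7.8). Seven of ten may leave (7/10 = 70%) with 3 remaining, or four of six (4/6 = 66.7%) with 2 remaining. One answer is then worth 1/3 = 33.3 or 1/2 = 50 points. These figures show how coarse the percentages are. They do not estimate bias.

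**7. The declaration in 10.7.** Sections iii, iv, 1 and 7.4 together make one person funder, analyst, degree candidate and lead therapist. Section 10.7 itself recognises a clinical conflict and handles it by not recruiting from the chief investigator's own cluster. That protects who is approached. It does not touch how the outcome is collected. The denial of any noncommercial potential conflict does not fit this account.

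**The case against.** A reader might infer that women answer by name, in front of the group, about the therapists personally, and that the ratings are therefore biased. The protocol does not support that chain. Section 10.6 provides pseudonyms. Section 7.7 gives no mode of completion. The items rate the group. Nothing in the document measures bias, and the 10 to 33 point figures apply to any item with so few respondents. Nor does the chief investigator make the first approach: under section 7.1 other professionals identify clients and ask about their interest.

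The stakes are also modest. The table in 3.3.4 describes the purpose as basic feedback, and no efficacy claim or decision is tied to it. The chief investigator's roles are openly stated elsewhere in the protocol, so the defect in 10.7 is one of wording and does not itself show bias in the ratings.

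Anonymity also has limits and costs. Therapists who have spent ten two-hour sessions with 6 to 10 women may recognise a writer from free text. Section 10.6 attaches quotes to a pseudonym or number, which an anonymous form would prevent. A disclosure of risk in anonymous free text could not be traced to anyone.

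All of this stands as a limit on the claim and as a list of what the remedy must address. It does not remove the gap: the form is asked on an occasion led by the therapists, no anonymous or independent return is stated, and the lead therapist can link and analyses the data.

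**Conclusion.** The point holds as a risk of bias towards approval in the sole secondary outcome of section 3. It rests on four features of the protocol: the occasion is led by the therapists, no anonymous return is stated, the chief investigator can link records and analyses them, and all items are worded favourably. It assumes that some women would answer more critically if they could not be identified, which is plausible but which the document cannot quantify. The size is unknown.

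The tempting conclusion that the ratings are biased, or are given by name, goes further than the text allows. The change is worth making because it is cheap and lowers a risk to a stated outcome. The primary scales are not affected by this point. The correction to 10.7 is a separate matter of accurate disclosure and would by itself change no result.

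**What to change.** **Section 7.7, with matching wording in the trial summary, 3.2 and 3.3.4.** State that the questionnaire is:
- completed outside the session on an anonymous online form, without name, number or pseudonym, opened at the eight-week point;
- sent by link to every woman who started the group, including those who miss the follow-up session;
- read by the therapists only after the form has closed;
- marked on its face as not monitored for risk.

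Report the number of links sent and forms returned, and present the ratings as feedback and not as evidence of efficacy. In the same edit, settle whether the item is primary or secondary and whether it belongs to the final or the follow-up session.

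**Section 10.6.** Add an exception for this questionnaire to the rule that quotes carry a pseudonym or number.

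**Section 10.7.** Remove the denial of noncommercial potential conflicts and disclose that the chief investigator funds, delivers and analyses the study as part of a degree.

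**Cost.** An online form and short edits in six places. Section 6.1 already requires each woman to have a suitable device. Feedback and its free text could no longer be tied to an individual's scores. Section 8 mentions associations in general terms but describes none involving the feedback. With 6 to 10 women, free text may still identify a writer, so anonymity will be partial.
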